Household Contacts (HHC)						
	ICF		x			
	Demography survey		x			
	Symptom check	x		x	x	x
	COVID19 PCR	x		x	x	x
	COVID serology	x		x	x	x
	Follow up surveys	x		x		x

Data Collection and Management: Data will be collected by study staff on handheld devices. Data will be downloaded daily to a central database housed at the DTHF head office. Further details are available in Work Package 5 and the Data Management document.

Statistical Analysis and sample size: We will describe and compare the characteristics and survey outcomes, isolation, and linkages of participants. We calculated the different effect sizes (Table 2). Based on exponential test for comparing hazards, assuming $120*6=720$ subjects, different intraclass correlation coefficients (ICCs) and comparing $R_0=2.5$ (with resulting incidence of 0.208 among 720 subjects) to a reduced R_0 of 0.9 (64% reduction, with resulting incidence of 0.075 among 720 subjects) or 1.25 (50% reduction) or 1.5 (40% reduction).

Table 3: ICC calculations

ICC	Ro 2.5 to 0.9	Ro 2.5 to 1.25	Ro 2.5 to 1.5
	64% reduction	50% reduction	40% reduction
0.05	1.00000	1.00000	0.999944
0.25	1.00000	0.999891	0.991312
0.50	0.999993	0.995042	0.935880
0.75	0.999729	0.972942	0.846222
0.90	0.999033	0.951485	0.792745

The analyses will be determined by the study analysis plan. These analyses include the calculation of the proportion of SARS-CoV-2 positive individuals screened over a 3-month period, the transmissibility of the virus by determining the proportion of SARS-CoV-2 transmitted to household contacts of the identified COVID19 cases over a 4-week period, the period of infectiousness by correlating the time to transmission and clinical symptoms of the index cases, and the symptomatic/asymptomatic ratio among transmitted SARS-CoV-2 in household contacts. The Ro will be determined by both looking at new cases among the population in contact with the index cases and the total population (both in our service and other clinics in the area) diagnosed over time. The main outcome relates to the incidence of new cases of COVID19. These will be analysed using mixed effect Poisson regression models and frailty models to take the clustering by household into account. Both these regression models take the duration of follow up into account. Scores (e.g., GHQ) will be baseline adjusted. Qualitative data will be transcribed, translated and inductively analysed for themes.

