8.3. The proportion of index patients and HHC that showed improved psychosocial functioning in the intervention arm as compared to the enhanced usual care (EUC) arm. 10	
8.4. The association between the time to transmission and clinical symptoms of the index cases.....	10
8.5. The symptomatic/asymptomatic ratio among transmitted SARS-CoV-2 in household contacts	10
8.6. The incidence of SARS-CoV-2 transmitted to HHC of the index COVID19 cases over a 4 week period, stratified by COVID-19 wave.....	10
8.7. Analysis of household exposure to SARS-CoV-2 at baseline using the baseline serology result, and development of antibodies using the serology result during follow-up. 10	
8.8. Process Evaluation Analysis.....	11

1. ***INTRODUCTION***

This Statistical Analysis Plan (SAP) describes the statistical methods to be used during the analysis and reporting of data collected for the TRACE study. This SAP should be read in conjunction with the Study Protocol (dated 15 December 2020), Case Report Forms (CRFs, Final Versions, dated 4 November 2020) and Data Management Plan (DMP, dated 18 June 2020).

2. ***OBJECTIVES OF THE STUDY***

2.1. **Primary objectives**

1. To measure frequency and timing of transmission of SARS-CoV-2 to household contacts.
2. To investigate the effect of an intensive infection mitigation intervention (STOPCOV) administered by lay health care workers on the household transmission of SARS-CoV-2.

[figure not shown]
2.2. **Secondary objectives**

1. To investigate the effect of the STOPCOV intervention on clinical outcomes and psychosocial functioning
2. To investigate the difference in transmission of SARS-CoV-2 to HHC stratified by COVID-19 wave (first or second wave)
3. To describe the household exposure to SARS-CoV-2 at baseline using the baseline serology result, and development of antibodies using the serology result during follow-up.
4. To assess acceptability, feasibility and contextual factors impacting intervention delivery (process evaluation), specifically:
 - a. To understand the acceptability and feasibility of the STOPCov intervention.
 - b. To understand how context shapes implementation of the STOPCov intervention at the level of households and individuals.
 - c. To provide explanations for observed trends in the trial findings.
 - d. To generate theoretical generalisations of how to optimise wider implementation of the STOPCov intervention to other households to reduce transmission of COVID-19.

3. ***DESIGN OF THE STUDY***

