 - c. Assessment data of psychosocial functioning (General Health Questionnaire 9 for mood; UCLA Loneliness Scale and a version of the Brief AIDS-Related Stigma scale adapted for COVID-19, at baseline and at week 4);
 - d. Results of serology (pos/neg, no titres) and nasopharyngeal swabs for PCR of HHCs at baseline, and at weeks 1, 2, 3 and 4);
2. Randomisation list
3. Qualitative and quantitative process data on intervention (STOPCOV database)
 - a. Number and duration of calls to households
 - b. transcripts from follow-up calls
 - c. SMS/WhatsApp data
 - d. transcripts from interviews with STOPCov counsellors and intervention/control index and HHC participants
4. Provincial health data(PID; all study participants and household contacts)

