4.2. Secondary Outcomes

- The proportion of index patients and HHC that visited a primary health clinic during the period of follow-up in the intervention arm as compared to the enhanced usual care (EUC) arm.
- The proportion of index patients and HHC that were hospitalised for COVID-19 during the period of follow-up in the intervention arm as compared to the enhanced usual care (EUC) arm.
- The proportion of index patients and HHC that died due to COVID-19 during the period of follow-up in the intervention arm as compared to the enhanced usual care (EUC) arm.
- The proportion of index patients and HHC that showed improved psychosocial functioning, defined as lower GHQ 12, UCL loneliness scores and Stigma scores, in the intervention arm as compared to the enhanced usual care (EUC) arm.
- The proportion of SARS-CoV-2 transmitted to HHC of the index COVID19 cases over a 4 week period, stratified by COVID-19 wave.
- The proportion of index patients and HHCs who developed antibodies during follow-up.
- Process Evaluation Outcomes:
 - Barriers and facilitators to implementation of the STOPCov intervention.
 - Identified contextual patterns within households that interact with the implementation of STOPCov intervention
 - Theoretical explanations of how different structural relations and mechanisms impact on intervention delivery and outcomes.
 - Generalizable inferences and predictions on how best to optimise the STOPCov intervention.

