7. ANALYSIS OF PRIMARY STUDY OUTCOMES

7.1. The proportion of SARS-CoV-2 transmitted to HHC of the index COVID19 cases over a 4 week period

SARS-CoV-2 infection in a HHC will be defined as a positive PCR or evolving positive serologic test in a HHC who had a negative PCR or negative serology at baseline. The incidence of SARS-CoV-2 infection in HHC will be calculated as the number of new cases divided by the person time at risk and 95% confidence intervals calculated based on the Poisson distribution adjusted for clustering by household. This incidence as well as the timing to transmission will be analysed using exponential shared frailty models taking the clustering by household into account and allowing for censoring. The start time will be the date of diagnosis of the index case and the event time the date of diagnosis of the HHC using the date of the first positive test based on PCR or serology. Models will include possible confounders including adjustment for baseline values.

7.2. The proportion of transmissions to HHC in the enrolled households of index COVID cases assigned to the infection mitigation intervention arm compared with the households in the enhanced usual care (EUC) arm.

The incidence of SARS-CoV-2 will be estimated for the different study arms and incidence of and timing to SARS-CoV-2 per study arm will be compared by including study arm in the exponential frailty models.

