8. ANALYSIS OF SECONDARY STUDY OUTCOMES

8.1. The proportion of index patients and HHC that were hospitalised for COVID-19 during the period of follow-up in the intervention arm as compared to the enhanced usual care (EUC) arm.

The binary outcome of hospitalisations for COVID-19 will be determined for the different study arms will be compared and analysed using a mixed effect logistic regression model.

8.2. The proportion of deaths in index patients and HHC due to COVID-19 during the period of follow-up in the intervention arm as compared to the enhanced usual care (EUC) arm.

The binary outcome of deaths in index patients and HHC for COVID-19 will be determined for the different study arms and will be compared and analysed using a mixed effect logistic regression model.

8.3. The proportion of index patients and HHC that showed improved psychosocial functioning in the intervention arm as compared to the enhanced usual care (EUC) arm.

The continuous outcome of psychosocial functioning in index patients and HHC for COVID-19 will be compared and analysed using linear regression.

8.4. The association between the time to transmission and clinical symptoms of the index cases

The incidence of transmitted SARS-CoV-2 infections to household contacts will be estimated and compared by the number and duration of clinical symptoms of the index patients. These symptom characteristics can also be included in the frailty models.

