8.5. The symptomatic/asymptomatic ratio among transmitted SARS-CoV-2 in household contacts

The proportion of symptomatic and asymptomatic transmitted SARS-CoV-2 infections will be calculated, overall, with 95% confidence intervals based on binomial or asymptotic normal distributions.

8.6. The incidence of SARS-CoV-2 transmitted to HHC of the index COVID19 cases over a 4 week period, stratified by COVID-19 wave.

The incidence of SARS-CoV-2 will be compared by COVID-19 wave using exponential frailty models and including an indicator of the wave in the model.

The COVID19 wave will be defined as follows:

- wave 1: date of diagnosis of index case between 1 May and 31 November
- wave 2: date of diagnosis of index case from 1 December onwards

8.7. Analysis of household exposure to SARS-CoV-2 at baseline using the baseline serology result, and development of antibodies using the serology result during follow-up.

Longitudinal weekly prevalence profiles of serology results will be summarized overall and by study arm. These profiles can be analysed using hierarchical mixed effect logistic regression models with both household and HHC as nested random effects. Time to development of antibodies can be analysed using exponential frailty models. Models will include baseline serology results.

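### SAP 8.3 does not carry over the Protocol's baseline adjustment of the psychosocial scores, and does not say whether the outcome is the week-4 score or the change

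*SAP*

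**What the plan says.** **Protocol, Statistical Analysis and sample size.** The commitment is short: "Scores (e.g., GHQ) will be baseline adjusted".

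**SAP 8.3.** The method is "The continuous outcome of psychosocial functioning in index patients and HHC for COVID-19 will be compared and analysed using linear regression". It gives no covariate, time point or household term. The heading of 8.3 speaks of a proportion who improved, while the text speaks of a continuous outcome.

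**SAP 4.2.** Improvement is "defined as lower GHQ 12, UCL loneliness scores and Stigma scores", without saying lower than what.

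**SAP 3, data source 1c.** The scales are the General Health Questionnaire, then "UCLA Loneliness Scale and a version of the Brief AIDS-Related Stigma scale adapted for COVID-19, at baseline and at week 4". Both measurements are therefore planned.

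**Baseline terms elsewhere in the SAP.** Section 7.1, on the infection models, ends: "Models will include possible confounders including adjustment for baseline values". Section 8.7, on serology, says: "Models will include baseline serology results". Nothing equivalent appears in 8.3.

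**SAP 1 and 5.** Section 1 asks for the SAP to be read together with the Protocol. Section 5 treats any analysis that differs from those in the final SAP as post-hoc, and says missing data will not be replaced.

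**The concern.** The effect of STOPCOV on psychosocial functioning is part of secondary objective 1. The Protocol promised an adjusted analysis, the data for it are collected, and the document that governs the analysis does not mention it.

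Three things are at stake:

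- **Precision.** A linear regression on arm alone gives a less precise estimate than one that also uses the baseline score.
- **Chance imbalance.** Only 60 households are randomised per arm, so some difference in baseline distress, loneliness or stigma will arise by chance. An unadjusted estimate carries part of it.
- **Freedom after the fact.** With the Protocol saying one thing and the SAP silent, both an adjusted and an unadjusted analysis could be defended once results are known. Under the SAP section 5 definition, the analysis that the Protocol promised could even be labelled post-hoc.

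**Working it through.** **No stated figure to reproduce.** Neither document gives a standard deviation, target difference, power or correlation for these scores. SAP Table 1 concerns transmission and does not bear on 8.3.

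**Inputs from the documents.** 60 households and 360 people per arm (SAP 3, Randomization and stratification), so 360/60 = 6 people per household.

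**Assumptions.** Correlation r between baseline and week 4 of 0.4, 0.5 or 0.7; equal variance at both times; the same r at household and individual level; household intraclass correlation (ICC) of the scores of 0.05 or 0.25; two-sided 5% test.

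**Step 1: does other SAP text supply the adjustment?** The sentence in 7.1 closes the paragraph on the infection frailty models. Section 8.7 states its own baseline term, which would be needless if 7.1 applied throughout. So nothing carries adjustment into 8.3.

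**Step 2: precision.** In units of the score variance, the variance of the outcome used for the arm comparison is:

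- week-4 score, unadjusted: 1
- change score: 2(1 − r)
- week-4 score adjusted for baseline: 1 − r²

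The equivalent sample factor is 1/(1 − r²) against the week-4 score, and 2(1 − r)/(1 − r²) = 2/(1 + r) against the change score.

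| r | 1 − r² | 2(1 − r) | Factor vs week-4 score | Factor vs change score |
|---|---|---|---|---|
| 0.4 | 0.84 | 1.20 | 1.19 | 1.43 |
| 0.5 | 0.75 | 1.00 | 1.33 | 1.33 |
| 0.7 | 0.51 | 0.60 | 1.96 | 1.18 |

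Adjustment gains on both readings, but the two factors move in opposite directions as r rises.

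**Step 3: chance imbalance.** The design effect is 1 + 5 × ICC. The SD of the baseline difference between arms, in score SDs, is √(2 × design effect / 360).

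- ICC 0.05: design effect 1.25, SD 0.083, 95% limit 1.96 × 0.083 = ±0.16 SD.
- ICC 0.25: design effect 2.25, SD 0.112, 95% limit ±0.22 SD.

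An unadjusted week-4 comparison carries about r times the imbalance. A change score carries (1 − r) times it, in the opposite direction, through regression to the mean. At r = 0.5 both are about 0.08 SD (ICC 0.05) or 0.11 SD (ICC 0.25) at the 95% limit.

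**Step 4: illustration in power.** Take an assumed true difference of 0.2 SD and a variance that allows for clustering. The effective number per arm is 360/1.25 = 288 or 360/2.25 = 160. Power is Φ(0.2 × √(n/2) / √(1 − r²) − 1.96), with r = 0 for the unadjusted week-4 score.

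| ICC | Unadjusted week-4 | Adjusted, r = 0.4 | r = 0.5 | r = 0.7 |
|---|---|---|---|---|
| 0.05 | 67% | 74% | 79% | 92% |
| 0.25 | 43% | 50% | 54% | 71% |

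**The case against.** The best case for the plan has four parts.

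**The commitment still stands.** The SAP is to be read with the Protocol, nothing withdraws the adjustment, and linear regression as a class of model includes regression on baseline. A reader might infer that the SAP revoked the adjustment or chose an unadjusted model on purpose. The documents do not show that; they show silence. What remains is that 8.3 does not specify the adjustment and section 5 makes an unspecified analysis post-hoc.

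**The outcome may be a change score.** Improvement defined as lower scores can naturally mean change from baseline. In that case baseline is already in the outcome, and it would be wrong to say that 8.3 ignores it. This stands. It alters the size of the gain (1.18 rather than 1.96 at r = 0.7), not its direction.

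**Randomisation protects the estimate.** A reader might infer that the unadjusted comparison is biased, or that a baseline difference passes in full into the result. Neither follows. Over repeated randomisations the estimate is unbiased, and only the fraction in Step 3 passes through.

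**Adjustment has conditions.** With no replacement of missing data, participants without a baseline score leave an adjusted model. The order of events is also unclear. The Process entry of the Protocol schema describes randomisation before the baseline questionnaire, and the design text says only that randomisation follows consent. A baseline score given after the arm is known is a less safe covariate. Both points stand and belong in the fix.

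**Conclusion.** The point holds as an omission with a real, modest cost. SAP 8.3 leaves out an adjustment that the Protocol promised and the data allow, and it leaves the form of the outcome open. On either continuous reading, the analysis as written is less precise than the promised one.

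The gain is equivalent to 1.19 to 1.96 times the sample against an unadjusted week-4 score, or 1.18 to 1.43 times against a change score, for r between 0.4 and 0.7. The documents give no value of r, so the true gain could be smaller against a week-4 score if r is lower. The factors also depend on r being the same between and within households, which nothing in the documents establishes.

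This is a secondary outcome, and the validity of the randomised comparison is not in question. The change should be made before database lock, when the SAP is to be signed off.

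**What to change.** Rewrite 8.3 so that, for each scale separately:

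- the outcome is the week-4 score;
- the model is a linear mixed model with arm, the participant's own baseline score on the same scale, and a household random intercept, in line with the mixed models of 8.1 and 8.2;
- the reported result is the adjusted mean difference between arms with its 95% confidence interval.

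The household term belongs in the same sentence because baseline adjustment does not deal with clustering. With six people per household, an ordinary regression tested at 5% would have a true error rate of 2 × [1 − Φ(1.96/√design effect)], about 8% at ICC 0.05 and 19% at ICC 0.25.

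Two additions are needed. State how participants without a baseline score are handled, given the no-replacement rule in section 5. Confirm that baseline scores were collected before allocation was known, or say what is done where they were not. The SAP should also name one version of the General Health Questionnaire, since section 3 and section 4.2 give different ones (9 and 12).

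The cost is a few sentences and no new data. The one downside is the possible loss of participants without a baseline score, which the stated rule should limit.

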8.5. The symptomatic/asymptomatic ratio among transmitted SARS-CoV-2 in household contacts

The proportion of symptomatic and asymptomatic transmitted SARS-CoV-2 infections will be calculated, overall, with 95% confidence intervals based on binomial or asymptotic normal distributions.

8.6. The incidence of SARS-CoV-2 transmitted to HHC of the index COVID19 cases over a 4 week period, stratified by COVID-19 wave.

The incidence of SARS-CoV-2 will be compared by COVID-19 wave using exponential frailty models and including an indicator of the wave in the model.

The COVID19 wave will be defined as follows:

- wave 1: date of diagnosis of index case between 1 May and 31 November
- wave 2: date of diagnosis of index case from 1 December onwards

8.7. Analysis of household exposure to SARS-CoV-2 at baseline using the baseline serology result, and development of antibodies using the serology result during follow-up.

Longitudinal weekly prevalence profiles of serology results will be summarized overall and by study arm. These profiles can be analysed using hierarchical mixed effect logistic regression models with both household and HHC as nested random effects. Time to development of antibodies can be analysed using exponential frailty models. Models will include baseline serology results.

